Reimbursement. For the brief school social ecology climate survey, adolescents will receive a pen/pencil (worth 10 Rand) as appreciation. In the open pilot, adolescents will receive 50 Rand (consisting of 25 Rand to offset time and 25 Rand to offset travel costs) for the baseline outcome assessment, 60 Rand (consisting of 35 Rand to offset time and 25 Rand to offset travel costs) for the 1-month outcome assessment and 70 Rand (consisting of 45 Rand to offset time and 25 Rand to offset travel costs) for the 6-month outcome assessment. In the open pilot, adolescents in the intervention arm only, also fill out questionnaires to help us evaluate the acceptability of the intervention; these questionnaires will occur after each session. Adolescents in the intervention arm only, will receive 50 Rand (consisting of 25 Rand to offset time and 25 Rand to offset travel costs) for attending the enrollment session and the satisfaction assessments filled out in the first session. Adolescents in the intervention arm only, will also receive 60 Rand (consisting of 35 Rand to offset time and 25 Rand to offset travel costs) for filling out satisfaction assessments after the second session. The second session requires a slightly higher reimbursement rate because participants fill out both questionnaires on their satisfaction with the second session as well as the overall program.

SPECIFIC AIM 3: FEASIBILITY PHASE – ASSESS FEASIBILITY OF *SAFE SOUTH AFRICA* IN TRIAL RCT

Goals. In Feasibility Phase (Aim 3) we will assess feasibility for a future R01 trial including the rigor of facilitator implementation of the intervention protocol by evaluating fidelity and competence, recruitment strategies, and tracking and tracing success. We will assess feasibility by testing *Safe South Africa* in a randomized controlled pilot trial with 1- and 6-month follow-up. Participants include a sample of N=60 male adolescents who will receive a behavioral group-based intervention to prevent HIV risk, IPV perpetration, and increase bystander behavior. Intervention participants will be compared to a control of ordinary usual care. The ordinary usual care condition will consist of a packet of existing available brochures on HIV and other sexually

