
Reimbursement. Adolescents will receive 50 Rand (consisting of 25 Rand to offset time and 25 Rand to offset travel costs) for the baseline outcome assessment, 60 Rand (consisting of 35 Rand to offset time and 25

Rand to offset travel costs) for the 1-month outcome assessment, and 70 Rand (consisting of 45 Rand to offset time and 25 Rand to offset travel costs) for the 6-month outcome assessment. In addition, adolescents will receive 50 Rand (consisting of 25 Rand to offset time and 25 Rand to offset travel costs) for the enrollment session and filling out the satisfaction assessments that occur after the first session. Adolescents in the intervention arm only, will receive 60 Rand (consisting of 35 Rand for time and 25 Rand for travel) for satisfaction assessments filled out after the second session.).

Sample Size and Power Considerations. The primary objective of this pilot is to test feasibility, acceptability, and generate meaningful effect size estimates for a future fully-powered RCT. A fully-powered study is not our aim. We believe 60 adolescents (30 adolescents per arm) is adequate to examine feasibility and acceptability. We increase sample size by 10% as a conservative estimate during baseline recruitment to 66 adolescents to account for loss to attrition; our previous HIV intervention trial with similar aged adolescents in similar settings had 100% retention at the last follow-up timepoint.^{45,192} We considered sample size needed based on the goals of increased condom use at last sex by a third or double as shown in other adolescent HIV behavioral trials,^{20,193,194} and reduced sexual assault by half as shown in our previous trials of the *SAFE* intervention. To examine moderate effects (e.g., 0.50) we would need 200 adolescents, or 100 adolescents per arm, beyond the scope of this pilot. Thus, we focus on rigorously testing acceptability and feasibility.

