Analysis. For acceptability, we conduct the same analysis as described for Aim 2, setting 80% reporting positive ratings as a marker of acceptability and examining process data on satisfaction with clarity, structure, content, delivery, location, and timing of the intervention. For feasibility, we evaluate fidelity, setting 80% fidelity as a marker of acceptability. We also evaluate feasibility in regards to attendance rates, treatment retention rate, retention during outcome timepoints, and balance during randomization. For these data, individual ANOVA will be conducted to compare groups (*SAFE South Africa* vs. Control) on the continuous variables of number of sessions attended. For treatment retention rate (dichotomous), a chi-square analysis will be used. For success of random assignment in equating groups, we compare groups on demographic characteristics and primary risk factors for HIV and IPV. If groups differ on any variables that show a relation to outcomes, outcome analyses will be conducted both with and without adjusting for these covariates. For trial outcomes, preliminary analyses will include studies of patterns of missing data, dropout rates, and correlations effect size estimates with small samples have large standard errors so we use pilot data to assess hypothesized intervention effects.¹⁹⁵ We will examine key variables for skewness, variability, missing data, and outliers, with transformations to achieve normality if needed. We will examine descriptive statistics for main outcomes and mediators with extreme scores or deviations from normality to be addressed in subsequent analyses. Baseline differences between groups on demographic variables will be examined using *t*-tests and variables that show differences will be included as covariates in outcome analyses. Generalized estimating equations (GEE) will be used to compare intervention and control group on the main study outcomes following intention-to-treat principles. In exploratory analysis, we look at directions of hypothesized effects for our outcomes. While we are underpowered to test mediation effects directly, we will explore differences between study arms in hypothesized mediating and moderating variables. We will obtain the between treatment condition effect size estimates (with 95% confidence intervals) at each assessment (e.g., Cohen's *d* or *h*) to help determine necessary sample size for future fully-powered RCT.¹⁹⁶

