Dissemination. In addition to peer review papers and conference presentations, we will develop research briefs for adolescents, school stakeholders, and policy makers. In Year 3, we will submit an R01 application for a fully powered clinical trial to test the efficacy of *Safe South Africa*.

F. OTHER ETHICAL CONSIDERATIONS

Additional ethical reviews. We have submitted an ethical review application to Brown University and provide their letter providing detail that we are able to proceed with Aim 1 with a planned re-review prior to Aim 2 and 3 (see Appendices).

Inclusion of Children. This study will include children. In Aim 1, we will include male adolescents aged 15-17 years (inclusive) for focus groups. In Aim 2, we will include male and female adolescents ages 13-18 (inclusive) for a brief school climate survey, and male adolescents aged 15-17 years (inclusive) for an open

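### Attendance and retention are primary feasibility measures, but they have no target, and the only tests named for them compare the arms, which cannot show whether a rate is adequate

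*Combined protocol and SAP*

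**What the plan says.** All references are to the Combined protocol and SAP, mainly Section E, Specific Aim 3.

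- **Objective.** Sample Size and Power Considerations makes feasibility and acceptability part of the pilot's primary objective and defends the size on that ground: "We believe 60 adolescents (30 adolescents per arm) is adequate to examine feasibility and acceptability".
- **Marks that exist.** The Analysis paragraph gives two: for acceptability, "setting 80% reporting positive ratings as a marker of acceptability"; for delivery, "For feasibility, we evaluate fidelity, setting 80% fidelity as a marker of acceptability".
- **Measures without a mark.** The same paragraph continues: "We also evaluate feasibility in regards to attendance rates, treatment retention rate, retention during outcome timepoints, and balance during randomization". No target follows, and none appears elsewhere.
- **Tests named.** For number of sessions attended, "individual ANOVA will be conducted to compare groups". Then: "For treatment retention rate (dichotomous), a chi-square analysis will be used". Retention at the outcome timepoints is listed separately from treatment retention and is given no test.
- **Control arm.** Goals: "The ordinary usual care condition will consist of a packet of existing available brochures". No control sessions are described there.
- **Intervals.** The Analysis paragraph plans 95% confidence intervals for the exploratory effect sizes. It mentions none for the acceptability, attendance or retention rates.
- **Tracking.** The Assessments paragraphs record who attends sessions and who completes each assessment, and add exit questionnaires for boys who leave early and for completers.
- **Next step.** Dissemination: "In Year 3, we will submit an R01 application for a fully powered clinical trial".

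**The concern.** A pilot's feasibility question is about levels: do enough boys come to both sessions, and do enough complete the 6-month assessment, for a full trial to work? The tests named here ask something else, namely whether the two arms differ. Two arms with equally poor retention and two arms with equally good retention give the same answer.

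For sessions attended the comparison is weaker still. One arm is offered two sessions and the other a packet of brochures, so a difference is built into the design and says nothing about whether attendance was sufficient.

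Without a target, whether an observed 70% or 80% is good enough will be settled once the number is known, by the team preparing the next application. Without an interval, a rate from 30 boys may be taken as firmer than it is. At stake is how well the pilot informs the retention allowance, tracking effort and delivery of the full trial.

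**Working it through.** **Inputs.** 30 boys per arm, 60 in total; 10% allowance, 66 recruited at baseline; 80% marks (Aim 3, Sample Size and Analysis). Earlier workshop trial: 83% back at four months, 78% at seven (Section C, evidence for the existing intervention). No significance level is stated; two-sided 0.05 is assumed.

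**1. The plan's own figure.** 60 × 1.10 = 66, as stated. Since 66 × 0.90 = 59.4, the allowance implies retention of roughly 90%. At the workshop trial's rates, 66 boys would leave 66 × 0.83 = 54.8 or 66 × 0.78 = 51.5.

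**2. What a between-arm chi-square can detect.** Let both arms have the same true rate p. The rejection probability is the sum, over all i and j from 0 to 30, of Bin(i; 30, p) × Bin(j; 30, p) for those tables whose Pearson p-value is below 0.05.

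| True rate in both arms | No continuity correction | With correction |
|---|---|---|
| 50% | 5.2% | 2.7% |
| 60% | 4.9% | 2.6% |
| 70% | 4.9% | 2.6% |
| 80% | 4.9% | 2.2% |
| 90% | 5.4% | 0.9% |

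Without correction the result hardly moves between losing half of each arm and losing a tenth. Even as a check for unequal loss the test is weak at this size: it detects 90% against 70% half the time, and 80% against 60% 39% of the time.

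**3. Precision of the rates.** The exact (Clopper-Pearson) limits are the 2.5% point of Beta(x, n − x + 1) and the 97.5% point of Beta(x + 1, n − x).

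| Observed | Rate | Exact 95% CI |
|---|---|---|
| 24/30 | 80% | 61.4% to 92.3% |
| 27/30 | 90% | 73.5% to 97.9% |
| 48/60 | 80% | 67.7% to 89.2% |
| 54/60 | 90% | 79.5% to 96.2% |

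**4. How an 80% mark on the point estimate behaves.** With n = 30 the mark is 24, and the pass probability is P(X ≥ 24).

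- True 60%: 1.7%.
- True 70%: 16%.
- True 80%: 60.7%, so it is missed 39.3% of the time.
- True 90%: 97.4%.

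With n = 60 (48 or more), as an illustration for overall retention, the pass probability is 0.1% at a true 60%, 5.7% at 70%, 57.6% at 80% and 99.4% at 90%. An absolute rule therefore separates poor from good retention at this sample size, which the between-arm test does not.

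**5. Fidelity.** Thirty boys in groups of 10 to 20 make two or three groups. With two sessions each, that is 4 to 6 sessions. Coding 10–15% of them gives 0.4 to 0.9 of a session, so a binomial interval has nothing to work on.

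**The case against.** The strongest reply is that the plan does not rely on these tests alone. It tracks attendance and completion, studies dropout and missing-data patterns, and asks leavers why they left. Its declared use is to inform the design of the next trial. Fidelity and acceptability have marks, and recruitment has a number (60, with 66 sought at baseline). The team also reports full retention in a similar South African trial.

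Much of this stands, and it limits what can be claimed. A reader might infer any of the following, and the documents do not support them:

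- **That equal, poor outcome retention would be tested and passed as no problem.** The chi-square is assigned to treatment retention; outcome retention has no named test. Nothing says that a non-significant difference means feasible.
- **That the R01 will go ahead whatever the pilot shows.** The submission is stated without a condition, but in a dissemination paragraph, and no text says it would proceed despite poor results.
- **That the pilot cannot answer its own question.** Two of its components have marks, and low rates would be seen.

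What the reply does not supply is a standard for attendance and outcome retention set before the data are seen. The 10% allowance is a planning value, not a criterion. The full-retention precedent sits beside 83% and 78% in the workshop trial. That trial was in US college men, so it is an imperfect guide, but it shows that a shortfall from 90% is possible.

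**Conclusion.** The point holds and should be acted on. For attendance and treatment retention the plan names a method that answers a different question from the one the pilot asks. For 1- and 6-month completion it names no method or target. The chi-square rejects about 5% of the time at any common rate from 50% to 90%, and the ANOVA on sessions has no meaningful control value. The primary rates are imprecise (61% to 92% for 24 of 30) and have no stated interval.

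This is a weakness in how feasibility will be judged, not a failure to collect the information. The figures assume 30 per arm, a two-sided 0.05 level, no continuity correction unless stated, and independent boys. Group delivery, and the statement under Randomization & Retention that the control arm comes from a different school, could make responses correlated and the true uncertainty wider. Applying 80% to retention is illustrative; the plan sets no such mark.

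**What to change.** In the Specific Aim 3 Analysis paragraph:

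1. Replace the ANOVA and chi-square as the feasibility analysis. Report the proportion attending both sessions among boys allocated to the intervention, and the proportions completing the 1-month and 6-month assessments, overall and by arm, each with an exact 95% CI.
2. Fix a target for each before the first randomisation. The value is the team's choice; the plan's own 80%, or the 90% implied by its allowance, are candidates. State whether the point estimate or a confidence limit is compared with it. The choice matters: a true 80% misses an 80% point-estimate mark 39% of the time at n = 30, while requiring the lower limit to reach 80% would fail even 27/30 (73.5%) and 54/60 (79.5%).
3. Keep a between-arm comparison of outcome retention only as a check for differential loss, noting its low power.
4. Give the acceptability rate an exact 95% CI. Report fidelity descriptively, because so few sessions are coded.
5. State that a missed target leads to a change in the R01 design, for example in tracking or delivery.

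The cost is about one paragraph, using data already being collected. The downside is that the pilot can then report a missed target.

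### At 30 to 33 boys per arm, baseline tests can show neither that the arms are alike nor that allocation failed; balance should be described, and allocation judged on process counts

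*Combined protocol and SAP*

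**What the plan says.** All of the analysis text is in E. Methods, Specific Aim 3, Analysis. Feasibility includes balance: "We also evaluate feasibility in regards to attendance rates, treatment retention rate, retention during outcome timepoints, and balance during randomization". The next step is "For success of random assignment in equating groups, we compare groups on demographic characteristics and primary risk factors for HIV and IPV". Two consequences of a difference are given, both about the outcome models. One is "If groups differ on any variables that show a relation to outcomes, outcome analyses will be conducted both with and without adjusting for these covariates". The other, later in the paragraph among the preliminary analyses for trial outcomes, is "Baseline differences between groups on demographic variables will be examined using *t*-tests and variables that show differences will be included as covariates in outcome analyses".

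Acceptability and fidelity each have an 80% marker in this section. Balance has no marker, no significance level, no number of variables and no rule for reading the result. No test is named for the HIV and IPV risk factors.

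On size, Sample Size and Power Considerations says "We believe 60 adolescents (30 adolescents per arm) is adequate to examine feasibility and acceptability" and then "We increase sample size by 10% as a conservative estimate during baseline recruitment to 66 adolescents to account for loss to attrition". Baseline comparisons could therefore rest on 30 or on 33 boys per arm.

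Randomization & Retention describes permuted blocks of varying length, but in the same paragraph places the control arm in another school.

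**The concern.** The question for the future trial is whether allocation can be carried out as planned. A baseline comparison answers this poorly in both directions.

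If the t-test is the yardstick, a clean table may be taken as showing that the arms were alike, although a sample of this size cannot support that. If boys are individually randomised and allocation is sound, every baseline difference is chance. The test then examines a null hypothesis that is true by design, and a significant result says nothing about the allocation procedure. With many variables, some significant results are to be expected.

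At stake is one declared feasibility result. Which covariates enter the outcome models is a separate matter.

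**Working it through.** **The plan's own figures.** No power or precision is given for the baseline comparisons. The nearest figures are in Sample Size and Power Considerations.

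- 66 recruited: 60 × 1.10 = 66. This reproduces.
- 100 per arm for an effect of 0.50: with n = 2(z₀.₉₇₅ + z_power)²/d² and d = 0.5, n is 63 per arm at 80% power, 85 at 90% and 104 at 95%. With 100 per arm, power is about 94%. The plan states neither alpha nor power, so its figure is unexplained rather than wrong. Nothing below depends on it.

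**Inputs.** n = 30 per arm, or 66/2 = 33 per arm with equal allocation. Assumed: two-sided 5% two-sample t-test, boys treated as independent within arms.

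**1. Smallest observed difference that is flagged.** In SD units this is t₀.₉₇₅ × √(2/n).

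- 30 per arm: 2.002 × 0.2582 = 0.517 SD. An observed 0.50 SD gives p = 0.058.
- 33 per arm: 1.998 × 0.2462 = 0.492 SD.

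These are also the approximate half-widths of the 95% interval for a standardised difference near zero. A table with no significant results is therefore compatible with differences of about half an SD.

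**2. A systematic difference of 0.5 SD.** Power comes from the noncentral t with noncentrality 0.5/√(2/n).

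| n per arm | Noncentrality | Power | Missed |
|---|---|---|---|
| 30 | 1.936 | 0.478 | 52% |
| 33 | 2.031 | 0.516 | 48% |

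At a 10% level and 30 per arm, power is 0.606 and 39% are missed. At 5%, a true difference of about 0.74 SD is needed for 80% power at 30 per arm, and 0.70 SD at 33. These rates apply to a true difference between the populations supplying the two arms, which could exist if arms follow schools.

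**3. Sound individual randomisation.** There is then no true difference to miss. Per variable, an observed difference of 0.5 SD or more arises by chance about 6% of the time at 30 per arm (p = 0.058, step 1). Across k independent variables, the chance of at least one p<0.05 is 1 − 0.95^k:

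- k = 5: 23%
- k = 10: 40%
- k = 20: 64%

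The plan gives no k, so these values are assumptions. Correlated variables lower the figures: simulations with pairwise correlation 0.3 gave 34–36% for k = 10 and 54–55% for k = 20.

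**The case against.** The strongest reply is that the plan contains no such rule. It says the groups will be compared. The t-tests appear later, for demographic variables, and serve to choose covariates. Where this section wants a verdict it sets a threshold, and for balance it sets none. That stands: a reader might infer that a non-significant test will be declared proof of equal arms, but this is not written. What the text supports is that the criterion is unspecified, that its wording speaks of success in equating the groups, and that the only baseline method named cannot show this.

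A second reply is that the 52% does not fit individual randomisation. That also stands. A reader might take it as the chance that a chance imbalance goes unnoticed. It is not; it applies only to a systematic difference. Nor can one say that a 0.5-SD difference is more likely than not to be missed, because at the 33 per arm planned for baseline recruitment the rate is 48%.

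A third reply is that the plan adjusts for differences and treats outcomes as exploratory. This answers a stronger inference, that the baseline tests would materially bias the outcome estimates. The size of any such bias would need a baseline–outcome correlation that the documents do not give, and analyses with and without adjustment are foreseen. Adjustment does not, however, change what is reported about randomisation.

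Finally, if arms follow schools, a baseline comparison is informative and process counts alone would not reveal school differences. That is why standardised differences belong in the report alongside the counts.

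**Conclusion.** The point holds as a minor improvement to how one feasibility result is defined and reported; it is not a serious defect. Read through t-tests at 30 to 33 per arm, balance would be flagged only above about 0.5 SD, so a clean result would not show that the arms are alike. A systematic 0.5-SD difference would be missed about half the time (52% or 48%). Under sound individual randomisation a significant difference would not show that allocation failed, and at least one would appear about 40% of the time with 10 independent variables.

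The figures assume a two-sided 5% level, and the last also assumes the number and independence of variables. Which case applies depends on whether boys or schools are allocated, and the randomisation paragraph leaves that unclear.

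**What to change.** 1. In Randomization & Retention, first reconcile the control arm's separate school with individual permuted-block randomisation. This determines whether baseline differences are chance or possibly systematic.
2. In the Aim 3 Analysis section, replace significance testing as the measure of randomisation success with a baseline table by arm. Give standardised differences (d or h, as already planned for outcomes) with 95% confidence intervals, and do not state that the arms were equated.
3. Judge feasibility of allocation separately on process counts: boys eligible, attending the enrolment session and randomised; final arm sizes; control-arm contamination, which the Design section already screens for; and departures from the block sequence.

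The cost is a wording change and a different table, with no extra participants. Departures from the block sequence are not among the items that the Assessments section says are tracked, so they need a simple log. The downside is that the pilot can no longer report that randomisation equated the groups.

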Design. This is a randomized controlled trial where participants are prospectively assigned to two arms (Safe South Africa) versus the control of ordinary usual care. This will be a single blind study. Intervention participants will not be blinded to the condition they are in (the intervention group will receive the intervention first, with the control group given standard usual care. Study staff (e.g. intervention team) will not be blinded to the condition. Study staff (e.g., outcome assessment team) who assess outcomes after the experimental intervention has been delivered will be blinded to the condition participants have been assigned to. Blinding will be broken for data analysis. To reduce the risk of contamination, or that blinding will be broken by participants communicating to each other, we will request that participants in the intervention keep all activities and discussions to themselves. We will also assess whether blinding was successful by checking for contamination at the outcome assessments at 1- and 6-months. There is no chance that participants in the control group would participate mistakenly in the intervention so we assess for contamination in terms of sharing of intervention materials between the intervention and control group. Participants assigned to the control group will be screened for contamination. We will adjust for any contamination effects in analyses. Although this is a feasibility and acceptability trial, thus not designed to be fully powered to measure effects, we set out to create a study design that carefully adheres to elements outlined in the Consolidated Standards of Reporting Trials (CONSORT) Statement.¹⁵⁸ This pilot study adheres to a single blind, randomized pilot trial design with the end goal of informing a future fully powered RCT corresponding to a Phase III clinical trial.

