Table 2: Outcome Measures and Assessment Timeline						
Outcome	Measures	Baseline	Session 1	Session 2	1-month	6-month
Acceptability	
 Session Evaluation Form¹⁶² Client Satisfaction Questionnaire¹⁶³ 		✓	✓		
HIV Risk Behavior & Intentions: HIV and STI status; HIV testing; frequency sex; number and type of partners; use of condoms	
 Items taken from South African trials & NIH's Adolescent Medicine Trials Network for HIV/AIDS Interventions 	✓			✓	✓
IPV Perpetration Behaviors: type, frequency and severity of IPV; sexual perpetration and aggression, dating violence	
 Childhood Sexual Victimization Questionnaire (CSVQ)^{164,165} Sexual Experiences (SES-SFP)⁴⁷ Assault Characteristics Questionnaire (ACQ)¹⁶⁴ Conflict in Adolescent Dating Relationships¹⁶⁶ 	✓			✓	✓
Bystander Intervention Behaviors: proactive bystander behavior; bystander efficacy and readiness	
 Sexual Social Norms Inventory (SSNI)¹⁶⁷ Bystander Behavior Scale¹⁶⁸⁻¹⁷⁰ (BBS) Intent to Help Scale (IHS)^{168,170} Bystander Efficacy Scale^{169,170} (BES) Interpersonal Reactivity Index (IRI)¹⁷¹ Stages of Change Scale (SOC)^{90,172,173} 	✓			✓	✓

	• Decisional Balance Scale (DB) ¹⁶⁹				
Co-variates: socio-demographics; economic status; household characteristics	
 Items from the South African 2011 Census Questionnaire & World Health Organization Food Security Questionnaire¹⁷⁴ Verbal Autopsy Questionnaire for AIDS orphanhood¹⁷⁵ 	✓		✓	✓

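### The Aim 3 analysis has two incompatible covariate rules, both triggered by observed baseline differences; it does not pre-specify adjustment for the baseline outcome or say how contamination will be handled

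*Combined protocol and SAP*

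**What the plan says.** All references are to E. Methods, Specific Aim 3, unless stated otherwise.

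- **Rule 1 (Analysis).** The arms are compared on demographics and on primary risk factors for HIV and IPV. Then: "If groups differ on any variables that show a relation to outcomes, outcome analyses will be conducted both with and without adjusting".
- **Rule 2 (Analysis).** Demographics are compared by t-test, and "variables that show differences will be included as covariates in outcome analyses".
- **Outcome model (Analysis).** GEE "will be used to compare intervention and control group on the main study outcomes following intention-to-treat principles". No model terms are listed.
- **Effect sizes (Analysis).** "We will obtain the between treatment condition effect size estimates (with 95% confidence intervals) at each assessment", as Cohen's d or h, to help size a fully powered trial.
- **Baseline data (Table 2 and Assessments).** The outcome questionnaire is given at baseline, 1 month and 6 months. Its HIV risk items include "frequency sex; number and type of partners; use of condoms".
- **Contamination (Design).** It is checked at the two follow-up assessments. "Participants assigned to the control group will be screened for contamination", and "We will adjust for any contamination effects in analyses". No method is given.
- **Purpose.** Sample Size and Power Considerations places effect size estimation in the primary objective. The Feasibility Aim in Study Aims calls the efficacy hypotheses exploratory and secondary.

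**The concern.** An analyst could follow either covariate rule and report a different adjusted effect for the same outcome, with nothing in the plan to say which is the main one. Both rules depend on which variables happen to differ between 30 and 30 boys. Under individual randomisation such differences arise by chance, so testing for them is a poor way to choose covariates. The variable most likely to predict a follow-up score is usually the same score at baseline. It is collected, yet no sentence gives it a fixed place in the model. It is also unclear whether d and h come from the model or from raw arm summaries; if raw, neither covariate rule reaches them.

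Contamination is a separate gap. It arises after randomisation, so the way it is adjusted for decides which comparison the arm effect represents.

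**Working it through.** **1. The rules side by side.**

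| Baseline variable | Rule 1 | Rule 2 |
|---|---|---|
| Demographic, differs, related to outcome | two analyses | one, adjusted |
| Demographic, differs, unrelated | not adjusted | adjusted |
| HIV/IPV risk factor, differs, related | two analyses | not considered |
| Does not differ | not adjusted | not adjusted |

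The rules agree only when nothing differs. The baseline value of an outcome could enter under rule 1, but only if it counts as a primary risk factor and happens to be imbalanced.

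**2. How often chance triggers a rule.** The plan gives no significance level for these tests; 0.05 is assumed. With k independent baseline tests and true balance, the chance of at least one flag is 1 - 0.95^k: 23% for k = 5 and 40% for k = 10.

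**3. How often the rules disagree.** Simulation with 30 per arm, individual randomisation and no true effect. Rule 1 is taken in its adjusted version.

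- Five independent demographics, each with assumed correlation 0, 0.1 or 0.2 with outcome: the covariate sets differ for 21.8%, 20.0% or 15.4% of outcomes. When they differ, the two estimates are a median 0.05-0.08 SD apart (90th percentile 0.12-0.15). The SD of the estimate is 0.258 unadjusted, 0.253-0.258 under rule 1 and 0.254-0.261 under rule 2. Bias is about zero.
- The same, with one to five risk factors also screened under rule 1 (assumed correlation 0.3-0.5 with outcome): the sets differ in about 24-32% of trials, and the 90th percentile gap is near 0.3 SD. The SD under rule 1 falls from about 0.26 to 0.24-0.25.

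The second setting is closer to the text, because rule 1 does screen risk factors. Neither percentage is a property of the plan alone; both move with the assumed number and strength of the variables.

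**4. What baseline adjustment could gain (continuous outcomes).** Inputs: 30 per arm, t(0.975, 58) = 2.002, and an assumed baseline to follow-up correlation r. Variance of the arm difference in SD units:

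- ignoring baseline: 2/30, half-width 2.002 × √(2/30) = 0.52
- baseline as covariate: (2/30)(1 - r²), half-width 0.49, 0.45, 0.37 at r = 0.3, 0.5, 0.7
- baseline as a repeated response with a common mean: also about (2/30)(1 - r²), so there is nothing further to gain.

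These figures treat the 60 boys as independent and individually randomised.

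**5. Contamination as a covariate.** If a contamination indicator can be positive only in controls, the arm coefficient in a linear model is the intervention mean minus the mean of uncontaminated controls. Suppose a share p of controls is contaminated, and the tendency to be contaminated has latent correlation ρ with outcome. With no true effect the coefficient then shifts by ρ·φ(z_p)/(1 - p), where φ is the normal density at the cut-off z_p that leaves p above it. At p = 0.10, φ = 0.1755:

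- ρ = 0.3: 0.3 × 0.1755/0.90 = 0.06 SD
- ρ = 0.5: 0.5 × 0.1755/0.90 = 0.10 SD.

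The corresponding ranges are 0.03-0.05 at p = 0.05 and 0.15-0.25 at p = 0.30. The shift is zero if contamination is unrelated to prognosis. Both p and ρ are assumptions; the documents give neither.

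**The case against.** The strongest reply is that this is a pilot. It is openly underpowered, its efficacy analyses look at direction, and the plan itself warns of large standard errors. With demographics alone, a median gap of 0.05-0.08 SD between rules is small beside a half-width of 0.52, and bias is about zero. That stands, and it limits the severity. It does not remove the conflict, because the effect sizes are part of the stated primary objective.

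Three stronger readings are tempting, and the documents do not support them.

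- **That the plan ignores the baseline outcome.** GEE with the same questionnaire at three visits can naturally carry baseline as a repeated response. What the text supports is that adjustment is not pre-specified.
- **That the plan breaches intention-to-treat through contamination.** No method is stated. A sensitivity analysis beside an unadjusted main result would be consistent with intention-to-treat. The conflict arises only if contamination enters the main model. Nor does the Design section say that only controls are asked: it also says "so we assess for contamination in terms of sharing of intervention materials between the intervention and control group".
- **That selecting covariates by testing biases the result or never helps precision.** Under individual randomisation bias is about zero, and rule 1 gains a little precision when prognostic risk factors are screened.

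It is also fair to object that the precision figures assume independent, individually randomised boys. The intervention is delivered in groups of 10-20, and Randomization & Retention says the control arm comes from another school. The figures are illustrative for that reason.

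**Conclusion.** The inconsistency is in the text and needs no assumption: two rules, different covariates, different numbers of analyses, no designated main result. Baseline-outcome adjustment is not pre-specified, and the contamination method is missing. This should be corrected, but it does not threaten the feasibility and acceptability conclusions.

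Its size is uncertain. Disagreement for about 15-22% of outcomes (demographics only) or 24-32% of trials (with prognostic risk factors) rests on assumed correlations and a 0.05 test level. The precision gain ranges from about nothing, if baseline is already a repeated response with a common mean, to a half-width of 0.37 instead of 0.52 at a correlation of 0.7. The contamination shift is conditional on a method that the plan does not state.

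**What to change.** 1. **Replace both covariate rules** with one main GEE on the 1- and 6-month responses, with terms for arm, visit, arm-by-visit and the baseline value of that outcome. Select no covariate by baseline testing; report balance descriptively.
2. **State that d and h come from this model**, with d standardised by the unadjusted SD and h taken from marginally standardised proportions.
3. **Provide for sparse or conditionally defined binary outcomes**, such as sexual perpetration or condom use at last sex. If the lowest male rate in the preliminary data (7%, in a younger sample) applied, 30 × 0.07 gives about 2 events per arm, and a baseline-adjusted logistic model may have no finite estimate. For each such outcome, name in advance either one related baseline measure or an unadjusted difference in proportions, with no cut-off chosen from trial data.
4. **Rewrite the contamination sentence in Design.** All boys are analysed as randomised, with no contamination term in the main model. The contamination rate is reported as a feasibility result. Contamination is used only in a labelled sensitivity analysis whose method is stated.
5. **Reconcile separately** the control arm from a different school with the randomisation of individual adolescents. If the arms are in different schools, baseline differences may be systematic, and no baseline adjustment can separate arm from school.

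The cost is a few sentences in Analysis and Design and minor programming. No new data are needed. The change is best made before outcome data are seen by arm.
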